## 21   **SECTION B: RESEARCH METHODOLOGY**

### 23   **B1. ABSTRACT**

24      Service members deployed to high altitude (HA; hypobaric hypoxia) regions of the world experience  
25      aerobic performance decrements. Factors contributing to hypoxia-associated aerobic performance  
26      decrements, include an alteration in carbohydrate oxidation to metabolize energy to support the muscle  
27      workload. However, research has failed to consistently demonstrate an ergogenic advantage of  
28      consuming supplemental carbohydrate during strenuous work at HA. Moreover, there is evidence that  
29      oxidation of exogenous carbohydrate during exercise is blunted under acute hypobaric hypoxic  
30      conditions compared to normoxia (1, 2). The mechanisms by which hypoxia suppresses exogenous  
31      carbohydrate oxidation are not known. A better understanding how hypoxia modulates energy  
32      substrate metabolism during exercise is necessary for appropriate design and implementation of  
33      nutritional interventions aimed at maintaining physical performance at HA. The primary objective of this  
34      study is to confirm that acute HA exposure decreases exogenous carbohydrate oxidation during  
35      steady-state aerobic exercise compared to SL, and explore if the mechanism inhibiting plasma glucose  
36      uptake is insulin dependent or independent. This randomized crossover study will examine substrate  
37      metabolic responses to ingesting supplemental carbohydrate during steady-state aerobic-type exercise  
38      at sea level (SL) and following acute (~5 h) exposure to HA (4,300 m) conditions in 10 healthy,  
39      recreationally active males between the ages of 18-39 yrs. Following a 48-hr muscle glycogen  
40      normalization period, volunteers will complete 80-min of metabolically-matched, steady-state aerobic  
41      (same absolute workload corresponding to  $\sim 55 \pm 5\%$  of  $\text{VO}_{2\text{peak}}$  at HA) exercise on a treadmill, and  
42      consume 145 g of glucose ( $1.8 \text{ g} \cdot \text{min}^{-1}$ ) at SL and HA. SL and HA trials will occur in the USARIEM  
43      hypobaric chamber and be separated by a minimum 7-d washout period. Glucose tracers will be used  
44      to assess glucose turnover, and contribution to exogenous and plasma glucose oxidation. Indirect  
45      calorimetry and urine collections will be used to determine total carbohydrate, fat, and protein oxidation  
46      during exercise at SL and HA. Serial blood draws will be collected during each trial to assess  
47      endocrine and circulating substrate responses to exercise, carbohydrate, and hypoxia. Muscle biopsies  
48      will be collected before and after steady-state exercise to examine muscle glucose transporter  
49      expression and translocation, glycogen status, and activity intramuscular enzymes in aerobic and  
50      anaerobic energy metabolism. The primary risks associated with this study include those associated  
51      with acute hypobaric hypoxia, exercise, blood draws, and muscle biopsies.

[figure not shown]
### 53   **B2. BACKGROUND AND SIGNIFICANCE**

1  
2 Ingesting carbohydrate during aerobic exercise conducted at SL increases exogenous carbohydrate  
3 oxidation and limits endogenous carbohydrate utilization (3-6). Only two previous studies have  
4 investigated how hypoxia affects oxidation of exogenous carbohydrate ingested during exercise, and  
5 the observations reported from those studies differ (1, 2). When carbohydrate was ingested during  
6 exercise at 77%  $\dot{V}O_{2max}$  in normoxia and hypoxia equivalent to 4,300 m, exogenous carbohydrate  
7 oxidation was the same (2). In contrast, when carbohydrate was ingested during lower intensity  
8 exercise (55%  $W_{max}$ , ~55-60%  $\dot{V}O_{2max}$ ), exogenous carbohydrate oxidation was lower at high altitude  
9 (HA; 3,375 m) than normoxia (1). The reasons for the discrepant effects of hypoxia observed in these  
10 studies on exogenous carbohydrate oxidation during exercise are not clear, but might reflect  
11 differences in the exercise intensities employed.

12  
13 Hypoxia reduces  $\dot{V}O_{2max}$  (7, 8), so in the experiments described above (1, 2), exercise was performed  
14 at lower absolute intensity and metabolic rate in hypoxia to maintain relative exercise intensity (i.e. %  
15  $\dot{V}O_{2max}$ ) the same as normoxia. However, from a scientific (9, 10) and practical perspective (the  
16 metabolic rate during physical activities is the same at SL and  
17 HA, notwithstanding differences in relative intensity (i.e., %  
18  $\dot{V}O_{2max}$ ). We believe that differences in substrate metabolism  
19 during exercise at HA and SL should be investigated at the  
20 same absolute workload in both conditions. In one of the  
21 aforementioned studies (2), Péronnet et al. also compared  
22 exogenous carbohydrate oxidation during exercise performed at  
23 the same absolute intensity and metabolic rate (i.e.,  $\dot{V}O_2 = \sim 2.2$   
24  $L \cdot min^{-1}$ , 11.6  $kca \cdot min^{-1}$ ) in normoxia (54%  $\dot{V}O_{2max}$ ) and hypoxia  
25 (78%  $\dot{V}O_{2max}$ ) equivalent to 4,300 m. When subjects consumed  
26 140 g of glucose during aerobic exercise that was metabolically  
27 matched exogenous glucose oxidation was numerically lower  
28 but not statistically different at HA compared to SL, while total  
29 and endogenous carbohydrate oxidation were significantly increased at HA compared to SL. Maximal  
30 exogenous carbohydrate oxidation rates are achieved between 51-64% of  $\dot{V}O_{2max}$  (11). Therefore, in  
31 this previous study (2), it is possible that exogenous carbohydrate oxidation was already maximal  
32 during the normoxic exercise trials and could not increase any further during the hypoxic exercise. In a  
33 recent investigation, our laboratory sought to examine whether oxidation rates of exogenous glucose  
34 would differ during exercise performed at the same absolute intensity in normoxic and hypoxic  
35 conditions at exercise intensities eliciting less than maximal exogenous carbohydrate oxidation rates at  
36 HA. Findings from this study (unpublished) indicated that exogenous glucose oxidation diminished by  
37 46% from SL to HA when participants consumed 144 g carbohydrate while walking on a treadmill for  
38 80-min at a fixed absolute workload ( $\dot{V}O_2 = \sim 1.7 L \cdot min^{-1}$ ; 55%  $\dot{V}O_{2max}$  at HA; **Figure 1**). While  
39 exogenous glucose oxidation was lowered in our investigations, endogenous carbohydrate oxidation  
40 was numerically but not statistically higher at HA compared to SL. These data suggested that the  
41 body's ability to oxidize exogenous glucose during exercise may be compromised during acute HA  
42 exposure.

[figure not shown]
Figure 1: Carbohydrate oxidation

43  
44 Decreased insulin sensitivity is one potential mechanism for diminished ability to oxidize exogenous  
45 carbohydrate oxidation at HA (12-15). Concomitant with the suppression of exogenous carbohydrate  
46 oxidation in acute hypoxia, we also observed that blood glucose levels rose higher and remained  
47 elevated during exercise despite two to four fold higher insulin concentrations during HA exercise  
48 compared to SL (**Figure 2**). Under normal physiological conditions, elevated blood glucose levels  
49 stimulates a rise in circulating insulin to induce translocation of glucose transporter 4 (GLUT4), resulting  
50 in the uptake of glucose intake the cell. Several other investigations (12-15) have also observed this  
51 phenomenon of impaired insulin sensitivity upon acute exposure to HA in young healthy individuals.  
52 Therefore, it is possible that insulin resistance at HA may be a mechanism suppressing exogenous  
53 carbohydrate oxidation. However, little is known regarding alterations in intramuscular processes that

1 may regulate alterations in glucose uptake into the cell at HA compared to SL. Investigation is required  
2 on molecular pathways that regulate insulin dependent and independent translocation of GLUT4 to  
3 better understand the potential mechanism that may govern alterations in carbohydrate metabolism.  
4

Figure 2: Glucose and insulin concentrations

[figure not shown]
\*Different than Sea Level;  $P < 0.05$

### 5 B3. MILITARY RELEVANCE

6  
7  
8  
9 Service members deployed to HA regions of the world experience aerobic performance decrements.  
10 Based on findings from our previous study, one contributing factor, at least during acute exposures to  
11 HA, is a decreased ability to oxidize exogenous glucose, with no difference in total and endogenous  
12 carbohydrate metabolism. During the initial exposure to HA there appears to be a diminished insulin  
13 sensitivity in response to carbohydrate consumption, resulting in a 46% reduction in exogenous glucose  
14 oxidation during exercise compared to SL.

15 Additionally, consumption of carbohydrate at HA did not minimize declines in physical performance  
16 compared to a matched non-nutritive placebo as determined by a 2-mile time trial (Figure 3). These  
17 data indicate that while dietary carbohydrate or carbohydrate supplementation may not support  
18 exercise performance during acute HA exposure.  
19 Though it was observed that exogenous glucose  
20 oxidations was lower during exercise at HA compared  
21 to SL, the mechanism leading to diminished exogenous  
22 glucose oxidation at HA remains unclear. The purpose  
23 of this study is to define the metabolic underpinnings  
24 for lower exogenous glucose oxidation to develop  
25 appropriate dietary recommendations and/or  
26 countermeasures to support acute HA military  
27 operations.  
28  
29  
30

Figure 3: 2-mile time trial

\*Different than Sea Level;  $P < 0.05$

### 31 B4. OBJECTIVES/SPECIFIC AIMS/RESEARCH QUESTIONS

#### 32 Objectives

33  
34  
35 Confirm results from our previous investigation that acute HA exposure decreased exogenous  
36 carbohydrate oxidation during steady-state aerobic exercise compared to SL, and explore if the  
37 mechanism inhibiting plasma glucose uptake is insulin dependent or independent.  
38  
39

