#### 40 Hypotheses

1 Exogenous carbohydrate oxidation will be lower at HA compared to SL during steady-state aerobic  
2 exercise at the same absolute workload, and potential regulation of diminished glucose uptake will be  
3 examined by insulin dependent or independent mechanisms.  
4

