#### 28 Plasma Glucose Turnover Calculations

29 For calculation of plasma glucose turnover the Steele equation with modifications for non-steady state  
30 will be used (28). Enrichment (E) will be expressed as mole percent excess (MPE); calculated as  
31  $(\text{TTR})/(1 + \text{TTR})$ , where TTR is the tracer to tracee ratio. Appropriate corrections for skewed  
32 abundance distribution and overlapping spectra will be made for the TTR of the glucose tracers, 6,6-  
33  $^{2}\text{H}_2$  glucose and U- $^{13}\text{C}$ -glucose (28). From these calculations, total glucose  $R_a$  will be comprised of  
34 rates of appearance of exogenous (i.e., ingested) glucose and of endogenous (i.e., hepatic glucose  
35 production and negligible renal glucose production or splanchnic glucose) glucose (28):  
36

$$37 \text{ Total glucose } R_a (\text{Total } R_a) = (F - ((pV \times ((C_2 + C_1) / 2) \times ((E_2 - E_1) / (t_2 - t_1)))) / ((E_2 + E_1) / 2)$$

$$38 \text{ Glucose } R_d = \text{Total } R_a - (pV (C_2 - C_1) / (t_2 - t_1))$$

$$39 \text{ Exogenous glucose } R_a (\text{Exo } R_a) = ((\text{Total } R_a + F) \times ((G_2 + GE_1) / 2) + (pV \times ((C_2 + C_1) / 2)) \times$$

$$40 ((G_2 - G_1) / (t_2 - t_1))) \text{ Endogenous glucose } R_a = \text{Total } R_a - \text{Exo } R_a$$

$$41 \text{ Metabolic Clearance Rate (MCR) = Glucose } R_d / ((C_2 + C_1) / 2)$$

42  
43 Where F represents the infusion rate of 6,6- $^{2}\text{H}_2$  glucose;  $pV$  is the effective volume of distribution for  
44 glucose,  $C_1$  and  $C_2$  are plasma glucose concentrations at  $t_1$  and  $t_2$ , respectively,  $E_1$  and  $E_2$  are plasma  
45 enrichments of 6,6- $^{2}\text{H}_2$  glucose at  $t_1$  and  $t_2$ , respectively, and  $E_d$  and  $E_p$  are tracer enrichments of U-  
46  $^{13}\text{C}$ -glucose from the test drink and plasma, respectively.  
47

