### Calculations of Exogenous and Endogenous Glucose Oxidation

Exogenous and plasma glucose oxidation will be calculated as (1):

Exogenous glucose (g/min) =  $\dot{V}CO_2 [(R_{exp} - R_{ref}) / (R_{exo} - R_{ref})] / k$   
Plasma glucose (g/min) =  $\dot{V}CO_2 [(R_{exp} - R_{ref}) / (R_{glu} - R_{ref})] / k$

where  $\dot{V}CO_2$  is in L/min,  $R_{exp}$  is the observed isotopic composition of expired  $CO_2$ ,  $R_{ref}$  is the isotopic composition of expired  $CO_2$  at rest before ingestion of the first dose of  $^{13}C$ -glucose,  $R_{exo}$  is the isotopic composition of the exogenous glucose ingested,  $R_{glu}$  is the isotopic composition of plasma glucose, and  $k$  (0.747 L/g) is the volume of  $CO_2$  provided by the complete oxidation of glucose. Total endogenous glucose oxidation can be calculated by subtracting exogenous glucose oxidation from total CHO oxidation. Endogenous glucose oxidation derived from muscle and liver can be determined by subtracting plasma glucose oxidation from total carbohydrate oxidation (muscle), and subtracting exogenous carbohydrate oxidation (liver) from plasma glucose oxidation (1). The first 40 min of steady-state exercise will allow for equilibration between the  $^{13}C/^{12}C$  in expired  $CO_2$  and the  $^{13}C/^{12}C$  in  $CO_2$  produced in tissues (30). Thus, endogenous glucose oxidation will only be calculated from samples obtained in the last 40 min of steady-state exercise (40 to 80 min).

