## 27 **B5.8 Statistical Analysis**

### 28 **B5.8.1 Sample Size Estimation**

29  
30  
31 Statistical power and sample size were determined from the effect size of exogenous  
32 carbohydrate oxidation ( $-14 \pm 8$  g/40-min exercise) that we previously observed at HA compared  
33 to SL. Using this information the sample size necessary to determine statistical significance  
34 between intervention arms is 7, with an alpha of 0.05 and 80% power. To account for greater  
35 variance in the response to altitude between volunteers and increased study power to 90%, 10  
36 volunteers will be enrolled to complete this investigation. Based on our previous studies we  
37 request to consent 30 individuals to complete 10.  
38

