### 39 **B5.8.2 Data analysis**

40  
41 Statistical analyses will be conducted using either SPSS (IBM Corp. Armonk, NY), SAS 9.3 (SAS  
42 Institute Inc., Carey, NC), or equivalent. Common descriptive statistics will be used to describe  
43 volunteer characteristics. Shapiro-Wilk tests will be used to determine normality of data. Paired t-  
44 test will be performed to determine main effects of phase (SL versus HA) for glucose turnover and  
45 glucose oxidation. Mixed model repeated measures ANOVA will be performed to determine main  
46 effects of time (baseline versus post-exercise), phase (SL versus HA) and time-by-phase  
47 interactions for glucose and insulin concentrations, GLUT4 translocation, glycogen, mRNA and  
48 microRNA, Western blots and enzyme activity. If interactions are significant, appropriate post-  
49 hoc correction will be used to examine these relationships. Correlation coefficients and multiple  
50 regression analysis will be used to evaluate relationships between study outcome measures. The  
51 alpha level will be adjusted for multiple comparisons, with the level for statistical significance set  
52 at  $P < 0.05$ .  
53

---

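### No planned analysis divides the altitude deficit in drink-glucose oxidation between reduced appearance in blood and events after entry, while the objective already presupposes inhibited uptake

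*Combined protocol and SAP*

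**What the plan says.** B4 (Objectives) sets two aims: to confirm the lower exogenous carbohydrate oxidation at HA that the sponsor's previous study observed, and to explore whether the "mechanism inhibiting plasma glucose uptake is insulin dependent or independent". The hypothesis keeps the same frame: "exercise at the same absolute workload, and potential regulation of diminished glucose uptake will be" examined by insulin-dependent or insulin-independent mechanisms. Neither text names delivery of drink glucose into the blood as a possible step. B3, by contrast, says that the mechanism is still unclear.

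The measurements are broader than the objective. Under Plasma Glucose Turnover Calculations, B5.4 splits total appearance into "rates of appearance of exogenous (i.e., ingested) glucose and of endogenous (i.e., hepatic glucose" and other minor sources, and also derives Rd and MCR. The oxidation section adds: "Exogenous and plasma glucose oxidation will be calculated as (1" followed by the two breath equations. It states that endogenous oxidation "will only be calculated from samples obtained in the last 40 min of steady-state exercise". No matching window is given for Exo Ra, Rd or MCR.

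B5.8.2 says that a paired "test will be performed to determine main effects of phase (SL versus HA) for glucose turnover and" glucose oxidation. The only joint analysis is general: correlation coefficients and multiple "regression analysis will be used to evaluate relationships between study outcome measures". It names no variables, ratio, contrast or rule for reading the turnover and oxidation results together. B5.8.1 sizes the study on exogenous oxidation alone.

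**The concern.** Lower exogenous oxidation at HA can arise in two places. Less drink glucose may reach the circulation (gastric emptying, absorption, splanchnic retention), or less of what arrives may be taken up and oxidised. Delivery is a live alternative in this design. Volunteers drink 1450 mL during exercise, starting with a 550 mL bolus, after about 5 h at 4,300 m. Section C6.1 says that symptoms of acute mountain sickness, which include nausea and sometimes vomiting, commonly appear within four to six hours.

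Two separate P values do not divide one deficit between two steps. A significant oxidation test beside a non-significant Exo Ra test fits a purely after-entry cause, but it also fits a mixed cause. At stake is the reading of the GLUT4, signalling and enzyme data from four biopsies per volunteer: whether they explain the whole deficit, part of it, or little of it.

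**Working it through.** **Inputs from the documents.** Change in exogenous oxidation -14 ± 8 g per 40 min, n = 7 for 80% power, n = 10 for 90% power, alpha 0.05 (B5.8.1). Earlier fall in exogenous oxidation 46% (B2). The documents give no SD for Exo Ra, so every SD for it below is an assumption.

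**1. The plan's own sample size.** Exact paired t-test, two-sided 0.05, noncentrality (14/SD)√n.
- If 8 g is the SD of the paired difference, n = 5 gives 82.8% power, n = 7 gives 96.8% and n = 10 gives 99.8%.
- If 8 g is the SD within each condition, with an assumed correlation of 0.25, the difference SD is 8√(2 × 0.75) = 9.8 g and n = 7 is the smallest n with at least 80% power.
- The stated pairs (n = 7, 80%) and (n = 10, 90%) correspond to difference SDs of about 11.0 g and 12.1 g.

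The stated n is thus reasonable and leaves room for extra variance. It says nothing about precision for Exo Ra.

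**2. Scale.** SL mean = 14/0.46 = 30.4 g per 40 min; HA mean = 30.4 - 14 = 16.4 g. This joins a 46% fall reported for an 80-min bout to a difference per 40 min, which is an assumption. On this scale 8 g is 8/30.4 = 26% of the SL mean.

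**3. Power of the separate Exo Ra test, n = 10.** Suppose that reduced appearance explains half of the 46% fall, so Exo Ra drops by 23%. Power is that of a paired t-test with noncentrality (drop/SD)√10:

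| Assumed SD of paired difference, % of SL mean | Power, 23% fall | Power, 46% fall |
|---|---|---|
| 26 (8 g carried over to Ra) | 69% | 99.8% |
| 30 | 58% | 99% |
| 40 | 37% | 90% |
| 50 | 26% | 74% |
| 60 | 19% | 58% |

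The 95% CI half-width is 2.262 × SD/√10: 19% of the SL mean at SD 26%, and 43% at SD 60%.

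**4. What the pair of tests can tell.** Simulation with n = 10, oxidation change -14 g (SD 8), assumed Exo Ra SD of 8 or 12 g and assumed correlation of 0.3 or 0.6. The table gives the share of trials with oxidation significantly different and Exo Ra not significant, and the power of a direct within-person contrast (oxidation change minus Exo Ra change, in grams):

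| True source of the deficit | Oxidation significant, Ra not | Power of contrast |
|---|---|---|
| All after entry | about 95% | 89-100% |
| Half before, half after | 30% (SD 8) to 62% (SD 12) | 37-78% |
| All before entry | 0.2% (SD 8) to 9% (SD 12) | 5% (no after-entry part; false-positive rate) |

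Separate tests distinguish the two extremes fairly well. They do not apportion a mixed deficit. The direct contrast addresses the right quantity but has only moderate power in the mixed case.

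**5. Are the data there?** Exercise runs from 320 to 400 min, so its last 40 min are 360-400 min. B5.4 schedules plasma for both glucose tracers at 360, 380 and 400 min, and breath samples from 360 to 395 min. The window can be matched without new sampling. However, the printed Exo Ra equation uses G and GE terms that are not defined, while Ed and Ep are defined beneath it and do not appear in it.

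**The case against.** The strongest reply is that the plan already tests uptake. Rd and MCR are turnover quantities, B5.8.2 compares turnover between SL and HA, and MCR bears directly on clearance from plasma. This stands. A reader might infer that the deficit cannot be placed before or after entry at all. The documents do not support that, because the needed quantities are derived for each volunteer. The gap is in the prespecified analysis and its interpretation.

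Second, the uptake focus is argued from data. B2 reports that blood glucose rose higher and stayed elevated at HA despite two- to four-fold higher insulin. Slower appearance alone would not be expected to produce that. This also stands, but it does not rule out a mixed cause, since glucose concentration reflects all appearance, including hepatic output, against disposal.

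Third, a reader might infer that the sponsor would credit the whole fall to muscle uptake, or would report a non-significant Ra as no change. Neither rule is written. B2 and B4 use cautious words and the mechanistic aim is exploratory. The plan simply has no rule against either reading.

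Fourth, a non-significant Ra result is not always the likelier one for a half-share effect. At assumed SDs of 26% and 30%, power exceeds one half. It falls below one half at 40% to 60%.

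Finally, oxidation relative to Ra falls with any after-entry cause, including storage or reduced pyruvate dehydrogenase flux. A lower ratio alone cannot identify uptake, and the fix has to respect that.

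**Conclusion.** The concern holds as a gap in the analysis plan. B5.8.2 names no analysis that apportions the oxidation deficit between reduced appearance of drink glucose and events after entry, and B4 words the mechanism as if reduced uptake were established. The general regression sentence does not fill the gap: it names no variables, and a correlation would not locate the step.

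The size depends on assumptions: a half share for appearance, a common SL scale of 30.4 g per 40 min, and Exo Ra difference SDs of 26% to 60% of the SL mean. Under these, the separate Ra test has about 69% down to 19% power. A non-significant result would thus be weak evidence that appearance is unchanged. The confirmatory comparison of exogenous oxidation is not affected. The change should be made, because it governs how the mechanistic data are read and costs little.

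**What to change.** 1. First correct the Exo Ra equation in B5.4, so that every term is defined and the defined drink and plasma enrichments are used or removed.
2. Add to B5.8.2 a within-volunteer SL-HA comparison of log(exogenous glucose oxidation / Exo Ra) over the matched 360-400 min window, with a 95% CI. Report it beside the 95% CIs for the SL-HA differences in Exo Ra, Rd and MCR over the same window.
3. State the reading rules in advance. A lower ratio at HA supports only an after-entry deficit. Reduced uptake is claimed only if MCR, read with insulin, is also lower at HA. A non-significant Exo Ra difference is not read as unchanged appearance.
4. Reword B4 along these lines: explore whether plasma glucose uptake is reduced at HA and, if so, whether the mechanism is insulin dependent or independent.

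Cost: a few lines of text and analysis, with no new samples or visits. The drawback is that the ratio carries the measurement error of both terms. For a mixed deficit, power is only moderate (37% to 78% for the similar gram-scale contrast in the working), so interpretation should rest on the CI and not on a P value.
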